### 1.3. Rationale for the study design

Participants of study V48P7E2 will be asked to participate in the current study. The aim of this study is to investigate the persistence of antibody response in adults up to 15 years after one *Encepur Adults* booster dose. Persistence of antibody response will be evaluated based on TBE-NT. Subjects with an NT titre below 10 at enrolment and subjects with a

decrease of NT titre to below 10 during the study will be invited to receive a booster vaccination. Data collected from this study may allow the provision of better information to prescribers who administer *Encepur Adults*, so that they can appropriately adjust the time of booster vaccinations to individuals who received different primary vaccination schedules and who live in TBE endemic regions.

## 1.4. Benefit : Risk Assessment

Please refer to the Prescribing Information for information regarding the summary potential risks and benefits of *Encepur Adults*.

The following section outlines the risk assessment and mitigation strategy for this study protocol:

### 1.4.1. Risk Assessment

Important Potential/Identified Risk	Data/Rationale for Risk	Mitigation Strategy
Investigational vaccine: Encepur Adults		
As with other vaccines there is a very rare risk of experiencing serious adverse events after vaccination with Encepur Adults such as severe allergic reactions (e.g. generalised urticaria, angioedema, stridor, dyspnoea, bronchospasm, hypotension)	A review of Encepur Adults safety data collected through spontaneous and solicited reports in the company safety databases concluded that the benefit-risk profiles of the vaccine continue to be positive.	Close monitoring of serious adverse events.
Study Procedures		
Risk of blood sampling	Blood sampling associated risk of syncope, dizziness, infection at the site after or during venepuncture.	Blood samples will be obtained by a trained professional and medical assistance will be available. The potential risk of feeling faint, or experiencing mild local pain, bruising, irritation or redness at the site where blood was taken, is mentioned in the ICF. The amount of blood to be taken for sampling will not be harmful to the subject's health.

Important Potential/Identified Risk	Data/Rationale for Risk	Mitigation Strategy
Study design		
Study is designed to collect yearly blood draws that will be analysed with NT. A booster dose (if NT titre <10) is possible 6 months (4-7 months) after blood draw.	There are standard timelines to allow sample analysis and release of laboratory results (most likely 6 months), and analysis of the data that cannot be avoided. But in case laboratory results are available earlier we add a broad time window of minus 60 days /plus 30 days (i.e. vaccination may be possible 4-7 months after blood draw) so that subjects can receive their booster dose as soon as possible.	TBEV is transmitted through the bite of infected ticks. Ticks are active from spring to autumn. Blood sampling is expected to be in autumn at scheduled visits and sera will be tested within 4-7 months, so that a booster dose can be given to subjects with NT titre <10 the following year, i.e. most likely before the beginning of the high risk period.

#### 1.4.2. Benefit Assessment

Benefits consideration may include:

- Appropriate timing for the administration of second booster dose; avoid administration of second booster dose if subject still has an NT titre  $\geq 10$ .
- Potential benefit of receiving a booster vaccination with TBE vaccine under controlled conditions (after determination of individual antibody titres and a booster vaccination only if antibody titres decreased to below 10).
- Medical evaluations/assessments associated with this study (such as physical examination, control of antibody against TBE titre).

#### 1.4.3. Overall Benefit:Risk Conclusion

Taking into account the potential and/or known risks identified, the potential benefits support the conduct of this study.

## 2. OBJECTIVES

### 2.1. Primary objective

- To evaluate the persistence of antibody response to a booster dose of *Encepur Adults* vaccine starting  $\geq 11$  years after the first booster administration and to continue following subjects up to 15 years after first booster administration.

Refer to Section 10.1 for the definition of the primary endpoints.

## 2.2. Secondary objectives

[figure not shown]
- To evaluate the immune response at 21 days after booster dose (boostability) in subjects with an NT titre below 10.
- To evaluate the safety of a booster dose with regard to SAEs collected after vaccination until study end.

Refer to Section 10.2 for the definition of the secondary endpoints.

## 3. STUDY DESIGN OVERVIEW

The study design of the current study along with the past 2 studies (primary and booster) is presented in the figures below. [Figure 1](#) presents the primary study, [Figure 2](#) presents booster study and [Figure 3](#) presents the current long term follow-up study.

**Figure 1 Study design of Studies V48P7**

[figure not shown]
**C** = Conventional schedule; **R** = Rapid schedule; **AC** = Accelerated Conventional schedule; **MC** = Modified Conventional schedule; **Rando** = randomisation; **LV** = Last Visit; **V** = Visit; **D** = Day; **VAC1**, **VAC2**, **VAC3** = vaccination 1, 2 or 3 (indicated in grey);

**Figure 2 Study design of study V48P7E1 and TBEV Polygeline-free-023 Ext:021 (V48P7E2)**

[figure not shown]

**TBE\_R\_B** = R-schedule in V48P7 and Booster before enrollment in V48P7E1; **TBE\_R** = R-schedule in V48P7 and Booster in V48P7E1; **TBE\_C** = C-schedule in V48P7 and Booster in V48P7E1; **TBE\_AC** = AC-schedule in V48P7 and Booster in V48P7E1; **C** = Conventional schedule in study V48P7; **R** = Rapid schedule study V48P7; **AC** = Accelerated Conventional schedule study V48P7; **Enrol** = Enrolment; **LV** = Last Visit; **V** = Visit; **D** = Day; **Y** = Year; **BVAC** = Booster Vaccination; **BS** = Blood Sample

\*Booster vaccination 3 years after primary vaccination in V48P7, except TBE R-B (vaccination before enrolment in V48P7E1 and BS only on Day 0)

\*\*Study group MC was not followed, it is not a registered schedule; \*\*\*last V48P7E1 visit is screening visit

**Figure 3 Study design of TBEV Polygeline-free-025 Ext:021**

TBEV POLYGELINE FREE-025 EXT:021 (205847)

**C** = Conventional schedule in study V48P7; **R** = Rapid schedule study V48P7; **AC** = Accelerated Conventional schedule study V48P7; **Enrol** = Enrolment; **VAC**=Vaccination; **LV**= Last Visit; **V** = Visit; **D** = Day; **Y** = Year; **BS** = Blood Sample; **SF** = safety follow-up

\* Approximate number of subjects planned for persistency, number of subjects with a NT titre below 10 during the study cannot be estimated.

\*\*Some or all of these visits may not be needed, depending on necessary booster vaccination of subjects.

Protocol waivers or exemptions are not allowed unless necessary for the management of immediate safety concerns. Therefore, adherence to the study design requirements, including those specified in the outline of study procedures (Section 5.5), are essential and required for study conduct.

- Experimental design: Phase IV, open-label, mono-centric study.
- Duration of the study: For each subject, the study will last less than 5 years.
  - Epoch 001: Persistence evaluation starting at Visit 23 (Year 11) and ending at Visit 27 or Visit 27.2.
- Primary completion Date (PCD): Visit 27.  
Refer to [GLOSSARY OF TERMS](#) for the definition of PCD.
- End of Study (EoS): Last testing results released of samples collected at Visit 27 or Visit 27.2.  
Refer to [GLOSSARY OF TERMS](#) for the definition of EoS.
- Study groups: Same groups as in study TBEV POLYGELINE FREE (V48)-023 EXT:021

**Table 1 Study groups and epochs foreseen in the study**

Study groups	Number of subjects*	Age	Epochs
			Epoch 001
C	51	25 years and above	x
R	46	25 years and above	x
AC	103	25 years and above	x

\* Approximate number of subjects

C: Conventional schedule: Primary vaccination of 66 subjects in study V48P7 on Days 0, 28 (+10) and 300 (+21), booster vaccination of 55 subjects in study V48P7E1, no vaccination in study TBEV POLYGELINE FREE (V48)-023 EXT 021 (V48P7E2).

R: Accelerated (or "rapid") schedule: Primary vaccination of 66 subjects in study V48P7 on Days 0, 7 (+3) and 21 (+7), booster vaccination of 9 subjects in study V48P7E1 (40 subjects received their booster vaccination before enrolment in study V48P7E1), no vaccination in study TBEV POLYGELINE FREE (V48)-023 EXT 021 (V48P7E2).

AC: Accelerated conventional schedule: Primary vaccination of 133 subjects in study V48P7 on Days 0, 14 (+3) and 300 (+21), booster vaccination of 109 subjects in study V48P7E1, no vaccination in study TBEV POLYGELINE FREE (V48)-023 EXT 021 (V48P7E2).

**Table 2 Study groups and treatment foreseen in the study\***

Treatment name	Vaccine/Product name	Study Groups		
		C	R	AC
Encepur Adults	Encepur Adults	X	X	X

\*Only subjects with an antibody titre below 10 at a scheduled visit.

- Vaccination schedule: Second booster vaccination six months (minus 60 days /plus 30 days) after the blood draw in subject with an NT titre below 10.

If a subject receives a booster dose in the study then he/ she will not have to come for any future scheduled visits. This subject will be included in the sub-cohort of subjects who received a booster dose. No further study procedures will be conducted after the blood sample collection 21 days post vaccination; however the subject will be followed up for safety until the study conclusion. Refer Sections 8.3.1 and 8.3.2.

- Treatment allocation: Independent from the study group, vaccination six months (minus 60 days /plus 30 days) after the blood draw only in subjects with an NT titre below 10.
- Sampling schedule: Blood samples to obtain neutralizing antibodies will be collected from all subjects at Visit 23 (Year 11), Visit 24 (Year 12 plus 15 days /minus 30 days), Visit 25 (Year 13 plus 15 days /minus 30 days), Visit 26 (Year 14 plus 15 days /minus 30 days) and Visit 27 (Year 15 plus 15 days /minus 30 days). Subjects who received a second booster vaccination will have an additional visit for a blood draw 21 days (plus 7 days) after the vaccination.
- Type of study: Extension of study TBEV POLYGELINE FREE (V48)-023 EXT:021 (V48P7E2).
- Data collection: Electronic Case Report Form (eCRF ).
- Safety monitoring: SAEs related to study participation, or to a concurrent GSK medication/vaccine will be collected for all subjects as of informed consent obtained for the entire duration of the study. For subjects who will receive their second booster dose in this study, all SAEs will be collected for 1 month after vaccination. Post-study SAEs will be collected until study conclusion (Refer Section 8.3.2).

## **4. STUDY COHORT**

### **4.1. Number of subjects/centres**

A total of approximately 200 subjects who participated in study TBEV POLYGELINE FREE (V48)-023 EXT 021 (V48P7E2), who received in a parent V48P7 study one of the following schedules: rapid (R), conventional (C), or accelerated conventional (AC) and a booster vaccination in study V48P7E1 or before study V48P7E1 (only R-schedule) and agreed to participate in this study are to be enrolled.

The number of subjects who will have a decrease of NT antibody titre to below 10 cannot be estimated. There is no information about the kinetics of NT antibodies until 15 years after booster vaccination with *Encepur Adults* available from clinical studies or publications.

**Table 3 Sub-cohorts**

Sub-cohort name	Description	Estimated number of subjects
Cohort for persistence	Subjects will come to the yearly scheduled blood draw visit for investigation of 11 to 15 year persistence of NT titres.	Approximately 200
Sub-cohort of subjects who received a second booster dose	Subjects who have an NT titre below 10 at one of the scheduled visits will receive a second booster dose 6 months after this visit at an unscheduled visit. Subsequent data of these subjects will be analysed separately in a subgroup.	*

\* Number of subjects who will need a second booster dose because their NT titres decreased to below 10 cannot be estimated.

### **Overview of the recruitment plan**

At the time of the initiation of this long term follow-up study, the investigator will contact all subjects who participated in study TBEV POLYGELINE FREE (V48)-023 EXT 021 (V48P7E2). The reason for non-participation in the long-term follow-up study will be documented in the site's screening log.

### **4.2. Inclusion criteria for enrolment**

Deviations from inclusion criteria are not allowed because they can potentially jeopardize the scientific integrity, regulatory acceptability of the study or subject safety. Therefore, adherence to the criteria as specified in the protocol is essential.

All subjects must satisfy ALL the following criteria at study entry:

#### **Inclusion criteria for all subjects**

- Subjects who, in the opinion of the investigator, can and will comply with the requirements of the protocol (e.g., return for follow-up visits).
- Written informed consent obtained from the subject prior to performance of any study specific procedure.
- Subjects who have participated in study V48P7E2 and who received in the parent V48P7 study one of the following schedules: rapid (R), conventional (C), or accelerated conventional (AC) and a booster vaccination in study V48P7E1 or before study V48P7E1 (only R-schedule)

#### **Additional inclusion criteria for subjects who will need a second booster dose**

- Healthy subjects as established by medical history and clinical examination before entering into the study.
- Female subjects of non-childbearing potential may be enrolled in the study. Non-childbearing potential is defined as pre-menarche, current bilateral tubal ligation or occlusion, hysterectomy, bilateral ovariectomy or post-menopause.

Please refer to the [GLOSSARY OF TERMS](#) for the definition of menarche and menopause.

- Female subjects of childbearing potential can receive the booster vaccine in the study, if the subject: has practiced adequate contraception for 30 days prior to vaccination, and has a negative pregnancy test on the day of vaccination, and has agreed to continue adequate contraception for 2 months after booster administration.

Please refer to the [GLOSSARY OF TERMS](#) for the definition of adequate contraception.

#### **4.3. Exclusion criteria for enrolment**

Deviations from exclusion criteria are not allowed because they can potentially jeopardize the scientific integrity regulatory acceptability of the study, or subject safety. Therefore, adherence to the criteria as specified in the protocol is essential.

The following criteria should be checked at the time of study entry. If ANY exclusion criterion applies, the subject must not be included in the study:

**Each subject must not be:**

- Unwilling or unable to give written informed consent to participate in the study.
- Perceived to be unreliable or unavailable to complete the study.

**Each subject must not have:**

- Clinical conditions representing a contraindication to blood draws.
- Any other clinical condition that, in the opinion of the investigator, might interfere with the results of the study or pose additional risk to the subject due to participation in the study.
- Received an investigational or non-registered medicinal product within 30 days prior to informed consent.
- Concurrently participating in another clinical study, at any time during the study period, in which the subject has been or will be exposed to an investigational or a non-investigational vaccine/product (pharmaceutical product or device).
- Levels of NT<10 in V48P7E2 study.
- Previous vaccination against TBE or other *Flavivirus* diseases with other TBE (comparator vaccines) and *Flavivirus* vaccines (e.g. Yellow fever vaccine, Dengue fever vaccine, Japanese encephalitis vaccine) before, during and after completion of the V48P7E2 and before starting TBEV POLYGELINE FREE-025 EXT 21 study.
- Primary immunization with TBE vaccine in the parent study V48P7 according to the modified conventional (MC) schedule.
- History of confirmed TBE infection.
- Known exposure (documented infection) to other Flaviviruses.

**Each subject who will receive the second booster vaccination in this study  
additionally to the exclusion criteria above must not have:**

- Hypersensitivity, including allergy, to any component of vaccines, medicinal products or medical equipment whose use is foreseen in this study.
- Clinical conditions representing a contraindication to intramuscular vaccination.
- Progressive, unstable or uncontrolled clinical conditions.
- Abnormal function of the immune system resulting from: Clinical conditions. Systemic administration of corticosteroids (PO/IV/IM) for more than 14 consecutive days within 90 days prior to informed consent. This will mean prednisone  $\geq 20$  mg/day (for adult subjects) or equivalent. Inhaled and topical steroids are allowed. Administration of antineoplastic and immuno-modulating agents or radiotherapy within 90 days prior to vaccination.
- Received immunoglobulins or any blood products within 180 days prior to vaccination.
- Administration of long-acting immune-modifying drugs at any time during the study period (e.g. infliximab).
- Acute disease and/or fever at the day of booster vaccination.
  - Fever is defined as temperature  $\geq 38.0^{\circ}\text{C}$  /  $100.4^{\circ}\text{F}$ . The preferred location for measuring temperature in this study will be the oral cavity.
  - Subjects with minor illness such as mild diarrhea or mild upper respiratory tract infection without fever (oral temperature  $<38.0^{\circ}\text{C}$ ) may be vaccinated at the discretion of the investigator.
- Expected general decrease in immune response, (eg, those who had sustained major injury or undergone recent major surgical operations, were undernourished, or had disorders involving a decreased immune response).
- Organic brain disturbances, including seizure disorders.
- Progressive neurological disorders.
- Suffered febrile or afebrile convulsions.
- Serious chronic illness (such as insulin dependent diabetes, cancer, autoimmune diseases).
- History of any reaction or hypersensitivity likely to be exacerbated by any component of the vaccine or chemically related substances.
- Individuals who received any other vaccines within 14 days (for inactivated vaccines) or 28 days (for live vaccines) prior to vaccination in this study or who are planning to receive any vaccine within 28 days from the study vaccines.
- Pregnant.

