# Will only be collected from subjects who received a second booster vaccination in this study, all SAEs will be collected for 1 month after vaccination.

Table 5 List of study procedures for ad hoc and additional visits

Timepoint(s)	Year 11		Year 12		Year 13		Year 14		Year 15	
Type of contact	Visit 23.1	Visit 23.2	Visit 24.1	Visit 24.2	Visit 25.1	Visit 25.2	Visit 26.1	Visit 26.2	Visit 27.1	Visit 27.2
	ad hoc visit 6 months after scheduled visit 23	21 days after ad hoc visit	ad hoc visit 6 months after scheduled visit 24	21 days after ad hoc visit	ad hoc visit 6 months after scheduled visit 25	21 days after ad hoc visit	ad hoc visit 6 months after scheduled visit 26	21 days after ad hoc visit	ad hoc visit 6 months after scheduled visit 27	21 days after ad hoc visit
Sampling timepoint(s)		post-vacc								
Check inclusion / exclusion criteria	•		•		•		•		•	
Medical history	•		•		•		•		•	
Physical examination	•		•		•		•		•	
Urine pregnancy test	•		•		•		•		•	
Check contraindications and warnings and precautions to vaccination	•		•		•		•		•	
Pre-vaccination body temperature	•		•		•		•		•	
Measure/record weight	•		•		•		•		•	
Vaccination										
Vaccine administration	•		•		•		•		•	
Date of vaccine administration	•		•		•		•		•	
30 minutes post booster injection assessment	•		•		•		•		•	
Laboratory Assays										
Blood sampling for antibody determination (~10 ml)		•		•		•		•		•
Safety assessments										
Record any concomitant medications/vaccinations	•		•		•		•		•	

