### 6.5. Contraindications to subsequent vaccination

The following events constitute absolute contraindications to administration of *Encepur Adults*. If any of these events occur during the study, the subject must not receive a dose of vaccine but may continue other study procedures at the discretion of the investigator.

- Anaphylaxis following any previous administration of vaccine.
- Pregnancy (see Section 8.2.1).
- Any condition that in the judgment of the investigator would make intramuscular injection unsafe.

The following events constitute contraindications to administration of *Encepur Adults* at that point in time; if any of these events occur at the time scheduled for vaccination, the subject may be vaccinated at a later date, within the time window specified in the protocol, or withdrawn at the discretion of the investigator.

- Acute disease on the day of booster vaccination (acute disease means moderate or severe illness with or without fever). The vaccine may be administered to subjects with minor illness such as mild diarrhoea or mild upper respiratory tract infection with oral temperature <38.0°C).

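### The steroid exclusion for second-booster recipients counts back from informed consent, so it covers none of the 90 days before any in-window booster

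*Protocol*

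**What the plan says.** Protocol section 4.3 has a separate list of exclusions for subjects who will receive the second booster. Three look-backs for drugs or blood products follow one another:

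- Systemic corticosteroids (prednisone at 20 mg/day or more, or equivalent): "for more than 14 consecutive days within 90 days prior to informed consent".
- Antineoplastic agents and related treatment, in the same bullet: "immuno-modulating agents or radiotherapy within 90 days prior to vaccination".
- The next bullet: "Received immunoglobulins or any blood products within 180 days prior to vaccination".

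The criterion on other vaccines later in the list also runs from vaccination. The clause on long-acting immune-modifying drugs covers the whole study period.

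Table 4 in section 5.5 marks informed consent at Visit 23 only, and Table 5 (ad hoc visits) has no consent row. The booster timing in section 3 is "Second booster vaccination six months (minus 60 days /plus 30 days) after the blood draw" for subjects with a titre below 10, followed by an "additional visit for a blood draw 21 days (plus 7 days) after the vaccination". Table 5 lists "Check inclusion / exclusion criteria" at each booster visit. Section 4.3 permits no deviation and says that "adherence to the criteria as specified in the protocol is essential".

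**The concern.** An exclusion that applies only to booster recipients should keep recent immunosuppression from affecting the booster response, so it has to be timed to the booster. Consent comes months or years earlier. Repeating the eligibility check at the booster visit does not help, because the same words still point back to consent.

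The clause then errs in both directions. A subject taking at least 20 mg/day of prednisone at vaccination does not meet it. A subject whose only course ended before consent does meet it, even for a booster more than four years later. This carries into the analysis through SAP section 5.2.2.1, where code 200/2010 removes subjects from the per-protocol set for breaching eligibility criteria. On this clause the code would miss the first subject and catch the second if boosted.

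The endpoint at stake is the 21-day response to the second booster. It is a secondary objective, and section 1.2 says the data will guide the timing of the second booster.

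**Working it through.** **Inputs**

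- Consent at Visit 23, taken as day 0 (Tables 4 and 5). Earlier consent would only widen the gap.
- Steroid look-back: day −90 to day 0 (section 4.3).
- Booster: six months, −60/+30 days, after a scheduled draw (section 3).
- Scheduled Visits 24 to 27: yearly from Visit 23, −30/+15 days (section 3, Table 6).
- Post-booster draw: 21 to 28 days after the booster (section 3).
- Section 6.7.2 steroid rule: 90 days before every blood draw.

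**Reproducing the plan's own window.** The risk table in section 1.4.1 gives the booster window as 4–7 months after the draw. Taking six months as 180 to 183 days:

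- Earliest: 180 − 60 = 120 to 183 − 60 = 123 days.
- Latest: 180 + 30 = 210 to 183 + 30 = 213 days.

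Counting in calendar dates gives 121–124 and 211–214 days. All of these agree with 4–7 months.

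**Overlap with the steroid look-back.** For a booster on day B, the 90 days before it run from B − 90 to B. These meet the interval from −90 to 0 only if B is less than 90. The smallest in-window B is 120, and its 90-day period opens on day 120 − 90 = 30 (day 33 with a 183-day half-year). The overlap is 0, with a gap of at least 30 days.

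**All five booster visits**, with a year of 365.25 days. For Visit 24.1 onward, the earliest day is 365.25k − 30 + 120 and the latest is 365.25k + 15 + 213, where k is years since Visit 23.

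| Booster visit | k | Days from consent | Overlap with look-back |
|---|---|---|---|
| 23.1 | 0 | 120 to 213 | 0 of 90 |
| 24.1 | 1 | 455.25 to 593.25 | 0 of 90 |
| 25.1 | 2 | 820.5 to 958.5 | 0 of 90 |
| 26.1 | 3 | 1185.75 to 1323.75 | 0 of 90 |
| 27.1 | 4 | 1551 to 1689 | 0 of 90 |

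The longest interval is 1689 / 365.25 = 4.62 years.

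**What section 6.7.2 reaches.** Counting back 90 days from the post-booster draw gives 90 − 21 = 69 or 90 − 28 = 62 days before vaccination. The earliest 21 to 28 of the 90 pre-booster days stay uncovered.

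**The case against.** The strongest reply is that other provisions already deal with the case that matters.

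- **Section 6.7.2.** A subject on steroids at the booster, with more than 14 consecutive days of use in the 90 days before the post-booster draw, meets this rule. The uncovered days are the earliest of the 90, and use that ended about two months before vaccination is a remote threat to a 21-day response. This largely stands for the per-protocol analysis. But the section says only that such use may affect evaluability, it does not stop the vaccination, and it removes nobody from FAS-2.
- **SAP code 230/2040.** This excludes subjects given medication forbidden by the protocol, which could make removal mandatory. It is doubtful that it applies, because section 6.7.2 does not forbid these drugs.
- **Recording.** Section 6.7.1 requires qualifying steroid use before blood draws to be recorded, along with nearly all medication from 7 days before to 28 days after the booster. Most affected subjects could therefore be identified. This stands, but it is not an eligibility rule.
- **Clinical discretion.** Nothing obliges the investigator to vaccinate. Section 4.3 also excludes interfering conditions, abnormal immune function due to clinical conditions, expected poor immune response and serious chronic illness. Section 6.5 adds "Any condition that in the judgment of the investigator would make intramuscular injection unsafe". These will catch some steroid users, but none sets a steroid dose or window.
- **Consent at the booster visit.** Section 5.2.1 mentions a signed consent form before treatment allocation at the booster visits. Neither procedure table schedules a second consent, so this reads as a precondition already met.

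The primary persistence objective does not depend on this clause, and the boostability analysis is descriptive. If steroids blunt the response, any bias would understate boostability.

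**Conclusion.** The clause is wrong as written. It covers 0 of the 90 days before the booster at all five booster visits, under every reasonable reading of six months. The result assumes a single consent at or before Visit 23 and boosters given within the stated window.

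The consequence is modest. The protocol says the number of subjects who will fall below 10 cannot be estimated, so the number affected is unknown. Section 6.7.2 and investigator judgement narrow the gap, and only a descriptive secondary endpoint is exposed. No safety harm can be shown from the documents. The change is desirable, and the study's conclusions do not hinge on it.

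**What to change.** In the section 4.3 corticosteroid clause for second-booster recipients, replace the reference to informed consent with vaccination. The clause then covers all 90 pre-booster days at every booster visit and matches the adjacent look-backs.

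Leave the blood-draw anchor in section 6.7.2 as it is, because it governs whether titres are evaluable, including in subjects who are never boosted.

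The cost is one phrase in a protocol amendment. An occasional steroid-treated subject will not be boosted within the study, and section 5.7.5 already leaves re-vaccination of such subjects to the investigator outside it.
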